### 3 ASSESSMENT OF ADVERSE EVENTS

#### Severity Categorization

The severity of AEs must be recorded during the course of the event including the start and stop dates. Events that increase in severity will have the severity updated and the highest severity will be assigned to the event. Worsening medical conditions, signs or symptoms present prior to initiation of investigational product, must be recorded as new AEs.

For example, if a subject reports mild intermittent dyspepsia prior to initiation of dosing with the investigational product, and the dyspepsia becomes severe and more frequent after first dose of a new AE of severe dyspepsia (with the appropriate date of onset) should be documented in the source.

The Investigator will assess the Grade of the AE per the NCI-CTCAE version 5.0 or higher.

Toxicities that are not specified in NCI-CTCAE will be defined as follows:

- Grade 1: mild; asymptomatic or mild symptoms; clinical or diagnostic observations only; intervention not indicated
- Grade 2: moderate; minimal, local, or noninvasive intervention indicated; limiting age-appropriate instrumental activities of daily living (ADL)
- Grade 3: severe or medically significant but not immediately life-threatening; hospitalization or prolongation of hospitalization indicated; disabling; limiting self-care ADL
- Grade 4: life-threatening consequences; urgent intervention indicated
- Grade 5: death related to AE

#### Relationship Categorization

A physician/Investigator must make the assessment of relationship to investigational product for each AE. The Investigator should decide whether, in his or her medical judgment, there is a reasonable possibility that the event may have been caused by the IP. If there is no valid reason for suggesting a relationship, then the AE should be classified as “not related”. Otherwise, if there is any valid reason, even if undetermined or untested, for suspecting a possible cause-and-effect relationship between the investigational product and the occurrence of the AE, then the AE should be considered “related”. The causality assessment must be documented in the source.

The following additional guidance may be helpful:

Term	Relationship Definition
Related	The temporal relationship between the event and the administration of the investigational product is compelling and/or follows a known or suspected response pattern to that product, and the event cannot be explained by the subject's medical condition, other therapies, or accident.

Not Related	The event can be readily explained by other factors such as the subject's underlying medical condition, concomitant therapy, or accident and no plausible temporal or biologic relationship exists between the investigational product and the event.
-------------	---

Another source of guidance is provided in the World Health Organization-Uppsala Monitoring Center (WHO-UMC) causality categories descriptions. When applying the WHO-UMC categories in this study any AE fitting the causality term of Possible or higher (Probable/Likely or Certain) should be considered related. Any AE fitting the causality term of Unlikely or lower (Conditional / Unclassified or Unassessable / Unclassifiable) should be considered not related.

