### **7.2.1.2 Independent Data Monitoring Committee**

An independent DMC, whose members who are not affiliated with the Sponsor or CRO, will be utilized during the study to monitor subject safety throughout study conduct. The DMC will have access to unblinded data to perform comparative analyses during study conduct. A DMC charter will be developed preceding study initiation, which will define DMC processes and meetings. The DMC will meet at regular planned intervals during study conduct and also meet ad hoc for any identified urgent safety findings. Additionally, the DMC charter will define when a pause in enrollment is required pending a DMC safety review. The following criteria will trigger a pause in enrollment pending a DMC safety review:

- Death in any subject in which the cause of death is judged to be related to the study drug by the Investigator.
- One occurrence of an AE of special interest, which will be defined as an SAE considered related to the study drug and consistent with the toxicity profile defined in the IB. For asapiprant, there are no known AEs of special interest.

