#### WHO-UMC Causality Categories

Causality term	Assessment criteria*
Certain	

• Event or laboratory test abnormality, with plausible time relationship to drug intake

• Cannot be explained by disease or other drugs

• Response to withdrawal plausible (pharmacologically, pathologically)

• Event definitive pharmacologically or phenomenologically (i.e. an objective and specific medical disorder or a recognized pharmacological phenomenon)

• Rechallenge satisfactory, if necessary

Probable / Likely	

• Event or laboratory test abnormality, with reasonable time relationship to drug intake

• Unlikely to be attributed to disease or other drugs

• Response to withdrawal clinically reasonable

• Rechallenge not required

Possible	

• Event or laboratory test abnormality, with reasonable time relationship to drug intake

• Could also be explained by disease or other drugs

• Information on drug withdrawal may be lacking or unclear

Unlikely	

• Event or laboratory test abnormality, with a time to drug intake that makes a relationship improbable (but not impossible)

• Disease or other drugs provide plausible explanations

Conditional / Unclassified	

• Event or laboratory test abnormality

• More data for proper assessment needed, or

• Additional data under examination

Unassessable / Unclassifiable	

• Report suggesting an adverse reaction

• Cannot be judged because information is insufficient or contradictory

• Data cannot be supplemented or verified

\* All points should be reasonably complied with

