11.1 Adverse events

Adverse events will be coded using MedDRA version 23.1 and will be graded according to the NCI-CTCAE version 5.0. AE summaries will be presented by primary SOC and PT.

Treatment-emergent Adverse events will be considered as any event or worsening of event with onset on or after receiving the first dose of study drug through Day 57.

Summaries will be presented by actual treatment and overall using the SAF. Although a PT or SOC may be reported more than once for a patient, each patient will only be counted once.

Number and frequencies of patients with TEAEs as well as number of events will be given by SOC and by PT within each SOC for the following:

- All TEAEs by treatment group
- Serious TEAEs by treatment group
- All TEAEs considered related by treatment group
- Serious TEAEs considered related by treatment group

QMS Document Name: Statistical Analysis Plan	Page 23 of 27
QMS No (include version ref): STF-015-GL.02	Document date: 09JUL2019
CONFIDENTIAL	

- All TEAEs by maximum severity and by treatment group
- TEAEs leading to death by treatment group
- TEAEs leading to study discontinuation of study drug by treatment group

Additionally, number and frequencies of patients with TEAEs as well as number of events will be presented by decreasing frequency for all TEAEs, serious TEAEs and TEAEs considered at least possibly related.

If severity is missing, the event will be graded as severe unless the event being recorded is leading to life-threatening or death and will be graded accordingly as grade 4 (life-threatening) or 5 (death). If relationship to study drug is missing, the event will be assessed as unrelated if it started before start of IMP; in all other cases it will be assumed to be related.

Patient listings will be provided for patients with adverse events, treatment emergent adverse events, serious adverse events, for all patients with adverse events leading to withdrawal of IMP, and for all adverse events leading to death.

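### Appendix 3's WHO-UMC mapping lets lack of information alone make an event not related, against its own lead rule and opposite to SAP 11.1's default for blank entries

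*Protocol*

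**What the plan says.** Protocol Appendix 3, section 3 (Relationship Categorization) asks a physician to choose between two codes, *related* and *not related*. Its lead rule makes an event *related* "if there is any valid reason, even if undetermined or untested, for suspecting a possible cause-and-effect relationship" with the investigational product. A short table then describes the two codes. *Not related* is for an event that other factors readily explain and that has no plausible temporal or biological link to the product.

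The section next adds the WHO-UMC scale, introduced as follows: "Another source of guidance is provided in the World Health Organization-Uppsala Monitoring Center (WHO-UMC) causality categories descriptions". For investigators who apply it, Possible and above become *related*. For the rest, "Any AE fitting the causality term of Unlikely or lower (Conditional / Unclassified or Unassessable / Unclassifiable) should be considered not related".

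The WHO-UMC Causality Categories table defines the two bracketed terms. Unassessable/Unclassifiable begins with "Report suggesting an adverse reaction" and continues "Cannot be judged because information is insufficient or contradictory". Conditional/Unclassified is an event or laboratory abnormality for which the table gives "More data for proper assessment needed, or" alternatively that further data are being examined.

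SAP 11.1 has a rule for events whose relationship entry is missing. They are unrelated if they began before study drug; "in all other cases it will be assumed to be related".

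**The concern.** The mapping treats two statements about the state of the file as if they were the lowest grades of likelihood. Neither term says that the drug is an improbable cause. One says that the evidence is still coming in, the other that it is inadequate or inconsistent. Coding both as *not related* turns absence of information into a finding against causality.

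This matters because several safety steps depend on the *related* code. One pause criterion in Protocol 7.2.1.2, for example, is "Death in any subject in which the cause of death is judged to be related to the study drug by the Investigator". The related-event tables would also rest on opposite defaults. A post-dose event with the causality field left blank counts as related, while the same event judged unassessable and entered under the mapping counts as not related.

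**Working it through.** No arithmetic settles this point. The check is to set the rules side by side and then trace one event through the plan.

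**Step 1. The mapping against the rest of its own section.**

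| WHO-UMC term | What the table says | Code under the mapping | Under the lead rule | Meets the *not related* description? |
|---|---|---|---|---|
| Unlikely | Timing makes a link improbable; disease or other drugs are plausible explanations | Not related | Consistent with not related | Broadly yes |
| Conditional/Unclassified | More data needed or under examination | Not related | Open until the data arrive | No: nothing says that other factors explain the event |
| Unassessable/Unclassifiable | A report suggesting a reaction; information inadequate or conflicting | Not related | Arguably related, since suspicion is the starting point | No, for the same reason |

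The conflict with the lead rule is plainest for Unassessable. The conflict with the *not related* description applies to both terms.

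**Step 2. The mapping against SAP 11.1.** The SAP rule acts only on a missing entry. The mapping supplies an entry, so the SAP rule is not invoked. The clause in SAP section 1 that gives the SAP precedence does not help, because the two rules never act on the same record. They do give opposite answers to the same situation, a post-dose event whose cause is not known.

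**Step 3. Trace of a serious post-dose event entered as *not related* through the mapping.**

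| Step | Where | Needs *related*? | Event reaches it? |
|---|---|---|---|
| DMC review prompted by an individual SAE | Protocol 4.5 | Yes | No |
| Enrollment pause for a death | Protocol 7.2.1.2, first criterion | Yes | No |
| Enrollment pause for an event of special interest | Protocol 7.2.1.2, second criterion | Yes | No, but none is known for asapiprant |
| SUSAR status; notice to regulators and sites | Appendix 3, sections 1 and 8 | Yes | No |
| SAE discovered after the study has completed | Appendix 3, SAE collection time frame | Yes | No |
| Related, serious related and at-least-possibly-related TEAE summaries | SAP 11.1 | Yes | No |
| SAE report to the sponsor within 24 hours | Appendix 3, section 4 | No | Yes, through 30 days after last dose (Day 14 + 30 = about Day 44 for a full course) |
| Scheduled DMC safety meetings, with unblinded data | SAP 4.8 (after 33, 100 and about 208 subjects); Protocol 7.2.1.2 | No | Yes |
| All, serious and fatal TEAE tables; deaths by principal cause | SAP 11.1 and 11.2 | No | Yes |

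**Step 4. Current status.** The SAP Addendum states that enrollment stopped before the interim analysis and that every enrolled patient has passed Day 28. The two pause rows are therefore largely moot. The SUSAR, post-study and tabulation rows are not affected by that statement.

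**The case against.** The strongest reply is that the mapping is optional. It is offered as a further source of guidance for those who use the WHO-UMC terms, and the physician must still judge each event under the lead rule. An unassessable report may already satisfy that rule. This stands, and it means that misclassification is possible but not automatic. It does not remove the defect, because the mapping is the only text that says how to code these two terms, and it points the wrong way.

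A second reply is that SAP 11.1 fills a blank field at analysis while Appendix 3 guides a recorded judgment. This also stands. The two differ in direction but do not contradict each other on one record, and the SAP default affects tables only. It never governed the pause, the DMC review or SUSAR reporting.

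A third reply is that Conditional is a temporary state and that Appendix 3 requires events to be followed to closure. That reduces the concern for Conditional events, although the documents do not say that causality is re-coded when the data arrive.

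Two stronger readings are tempting. One is that poorly documented deaths and SAEs escape DMC review altogether. The documents do not support this: only the event-triggered review depends on *related*, and the scheduled unblinded meetings and all-causality tables do not. The other is that one can calculate the chance of such a death being missed. The documents give neither an expected mortality nor a rate of unassessable events, and the planned 312 is not a safe base once enrollment has stopped. Nor does anything show that a death coded this way would otherwise have been judged related.

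**Conclusion.** The point holds as a classification defect of limited reach. Appendix 3 allows two insufficient-information terms to be coded *not related*. That disagrees with the lead rule and the *not related* description in the same section, and it runs opposite to the SAP's default for blank entries. An event coded this way drops out of the steps marked as needing *related* in the trace and stays in the remaining three.

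Its size in events cannot be stated from the documents. The conclusion assumes only that at least some investigators use the mapping as written. It does not affect the primary efficacy analysis. For the related-event tables it lowers the count in whichever arm the events occur. The comparison between arms would be distorted only if such events were unequally spread.

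**What to change.** - **Protocol Appendix 3, section 3.** Remove Conditional/Unclassified and Unassessable/Unclassifiable from the *not related* group, leaving Unlikely. Reconcile the mapping with the lead rule, so that lack of information alone does not produce *not related*.
- **SAP 11.1.** State that post-dose events still unclassified or unassessable at database lock are tabulated under the existing missing-relationship default, that is as related, and report their number separately by arm.
- **Protocol 7.2.1.2.** The sponsor must reconcile how such events interact with the pause criterion. A blanket rule carried over from the tables could trigger a pause for a death that is only awaiting data. This review proposes no rule for that step.

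The cost is a few sentences in each document and in the CRF guidance, possibly a few more expedited reports, and a slightly higher related-event count in both arms. The documents do not say whether the WHO-UMC term is held in the database. If it is not, the separate count would need the source causality assessments to be checked. The SAP change remains useful with enrollment closed.

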#### WHO-UMC Causality Categories

Causality term	Assessment criteria*
Certain	

• Event or laboratory test abnormality, with plausible time relationship to drug intake

• Cannot be explained by disease or other drugs

• Response to withdrawal plausible (pharmacologically, pathologically)

• Event definitive pharmacologically or phenomenologically (i.e. an objective and specific medical disorder or a recognized pharmacological phenomenon)

• Rechallenge satisfactory, if necessary

Probable / Likely	

• Event or laboratory test abnormality, with reasonable time relationship to drug intake

• Unlikely to be attributed to disease or other drugs

• Response to withdrawal clinically reasonable

• Rechallenge not required

Possible	

• Event or laboratory test abnormality, with reasonable time relationship to drug intake

• Could also be explained by disease or other drugs

• Information on drug withdrawal may be lacking or unclear

Unlikely	

• Event or laboratory test abnormality, with a time to drug intake that makes a relationship improbable (but not impossible)

• Disease or other drugs provide plausible explanations

Conditional / Unclassified	

• Event or laboratory test abnormality

• More data for proper assessment needed, or

• Additional data under examination

Unassessable / Unclassifiable	

• Report suggesting an adverse reaction

• Cannot be judged because information is insufficient or contradictory

• Data cannot be supplemented or verified

\* All points should be reasonably complied with

#### Outcome Categorization

The outcome of AEs must be recorded in the Case Report Forms during the course of the study. Outcomes are as follows:

- Fatal
- Not Recovered/Not Resolved
- Recovered/Resolved
- Recovered/Resolved with Sequelae
- Recovering/Resolving
- Unknown

## 4 SAFETY REPORTING

### Reference Safety Information

The reference for safety information for this study is the Investigator Brochure which the Sponsor has provided under separate cover to all Investigators.

### Reporting Procedures

**SAEs that occur from the time of signing the ICF through 30 days after last dose of study drug require that a SAE report form be completed in the electronic data capture (EDC) system and submitted to the Sponsor or designee within 24 hours of the Investigator's first knowledge of the event, even if the experience does not appear to be related to study drug. In the event that EDC is unavailable, the SAE paper report form must be filled out by the Investigator and sent via email within 24 hours of awareness of the event to the [REDACTED]  
[REDACTED], and then the information entered into the EDC once available.**

## **SERIOUS ADVERSE EVENT COLLECTION TIME FRAME**

All SAEs occurring in patients will be recorded in the eCRF from the time of signing the ICF through the Safety Follow-up visit or 30 days after the last dose of study drug.

In addition, any SAE(s) considered “related” to the investigational product and discovered by the Investigator at any interval after the study has completed must be reported to the CRO using EDC data entry within 24 hours of the first becoming aware of the event.

## **SERIOUS ADVERSE EVENT ONSET AND RESOLUTION DATES**

The onset date of the SAE is defined as the date the event meets serious criteria. The resolution date is the date the event no longer meets serious criteria, the date the symptoms resolve, or the event is considered chronic. In the case of hospitalizations occurring after discharge from the original hospitalization at the time of study qualification, the hospital admission and discharge dates are considered the onset and resolution dates, respectively.

In addition, any signs or symptoms reported by the subject after signing the informed consent form, or leading up to the onset date of the SAE, or following the resolution date of the SAE, must be recorded as an AE, if appropriate.

## **FATAL OUTCOME**

Any SAE that results in the subject's death (e.g., the SAE was noted as the primary cause of death) must have fatal checked as an outcome with the date of death recorded as the resolution date. For all other events ongoing at the time of death that did not contribute to the subject's death, the outcome should be considered not resolved, without a resolution date recorded.

For any SAE that results in the subject's death or any ongoing events at the time of death, unless another investigational product action was previously taken (e.g., drug interrupted, reduced, withdrawn), the action taken with the investigational product should be recorded as "dose not changed" or "not applicable" (if the subject never received investigational product). The investigational product action of withdrawn should not be selected solely as a result of the subject's death.

## 5 PREGNANCY

All pregnancies are to be reported from the time informed consent is signed until the last follow-up visit.

Any report of pregnancy for any female study participant or the partner of a male study participant must be reported within 24 hours to the CRO. The pregnant female study participant must be withdrawn from the study.

Every effort should be made to gather information regarding the pregnancy outcome and condition of the infant. It is the responsibility of the Investigator to obtain this information within 30 calendar days after the initial notification and approximately 30 calendar days post-partum.

Pregnancy complications such as spontaneous abortion/miscarriage, elective abortion or congenital abnormality are considered SAEs and must be reported using the EDC.

In addition to the above, if the Investigator determines that the pregnancy meets serious criteria, it must be reported as an SAE using the EDC. The test date of the first positive serum/urine  $\beta$ -HCG test or ultrasound result will determine the pregnancy onset date.

## 6 ABUSE, MISUSE, OVERDOSE, AND MEDICATION ERROR

Abuse, misuse, overdose, or medication error (as defined below) must be reported to the Sponsor (or a nominated designee) according to the SAE reporting procedure whether or not they result in an AE/SAE.

Note: The 24-hour reporting requirement for SAEs does not apply to reports of abuse, misuse, overdose, or medication errors unless these result in an SAE.

The categories below are not mutually exclusive; the event can meet more than 1 category.

- **Abuse** – Persistent or sporadic intentional intake of investigational product when used for a non-medical purpose (e.g., to alter one's state of consciousness or get high) in a manner that may be detrimental to the individual and/or society
- **Misuse** – Intentional use of investigational product other than as directed or indicated at any dose (Note: this includes a situation where the investigational product is not used as directed at the dose prescribed by the protocol)
- **Overdose** – Intentional or unintentional intake of a dose of investigational product higher than the protocol-prescribed dose
- **Medication Error** – An error made in prescribing, dispensing, administration, and/or use of an investigational product. For studies, medication errors are reportable to the Sponsor only as defined below.

Cases of subjects missing doses of the investigational product are not considered reportable as medication errors.

Medication errors should be collected/reported for all products under investigation.

The administration and/or use of the unassigned treatment is/are always reportable as a medication error.

The administration and/or use of an expired investigational product should be considered as a reportable medication error.

